#### **4.3.5 Laboratory Evaluations**

Chemistry and Hematology parameters will be summarized using descriptive statistics for each visit. Both actual values and changes from baseline will be summarized.

The number and percentage of subjects meeting criteria for hepatobiliary abnormalities and for potential renal impairment will also be provided.

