
Statistical methods:
 
Safety and efficacy results will be summarized and presented by visit, with no inferential statistics presented. Parameters related to safety and tolerability will be treated as primary analysis variables. Efficacy parameters will be treated as secondary endpoints.
 
All data will be summarized by visit, with presentations based on the nature of the parameter. For binary data such as presence or absence of treatment-emergent adverse events, the incidence will be presented along with the overall number of subjects and percentages. External clinical laboratory and similar externally sourced data will be summarized as binary outcomes based on the determination of values beyond applicable normal ranges, and in some cases the assessment of clinical significance of deviations from normal ranges. For ordinal categorical data including efficacy data from PGA, EASI, SPA and SAD scores, and continuous data such as affected body surface area, summary statistics will be presented including N, mean, median, standard deviation, and standard error, by visit. Where applicable, the mean changes from baseline for ordinal categorical and continuous parameters will be presented by visit, along with N, median, standard deviation and standard error.

Analysis of Efficacy Outcome Measures:
 
Subject responder analyses will be conducted, by visit, based on the following criteria:
 
• The proportion of subjects whose active-treated lesions are judged to be clear or near clear on the PGA (PGA = ≤ 1) with a 2 grade or greater improvement from a baseline score of PGA=3 or PGA =4;• The proportion of subjects whose active-treated lesions are judged to be clear on the PGA (PGA = 0);

- The proportion of subjects who had an improvement from baseline of at least 75% in EASI score (EASI – 75).

Other subject responder criteria will be established as appropriate from data observation and the results will be presented as above.

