6. TRIAL OUTCOME MEAURES AND PURPOSE

6.1. Primary Outcome Measure

The primary outcome measure for this study is to assess the safety and tolerability of ATI-502 Topical Solution, 0.46% in subjects with moderate to severe atopic dermatitis.

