14. STATISTICS

14.1. Statistical Methods

Safety and efficacy results will be summarized and presented by visit, with no inferential statistics presented. Parameters related to safety and tolerability will be treated as primary analysis variables. Efficacy parameters will be treated as secondary endpoints.

All data will be summarized by visit, with presentations based on the nature of the parameter. For binary data such as presence or absence of treatment-emergent adverse events, the incidence will be presented along with the overall number of subjects and percentages. External clinical laboratory and similar externally sourced data will be summarized as binary outcomes based on the determination of values beyond applicable normal ranges, and in some cases the assessment of clinical significance of deviations from normal ranges. For ordinal categorical data including efficacy data from PGA, EASI, SPA and SAD scores, and continuous data such as affected body surface area, summary statistics will be presented including N, mean, median, standard deviation, and standard error, by visit. Where applicable, the mean changes from baseline for ordinal categorical and continuous parameters will be presented by visit, along with N, median, standard deviation and standard error.

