## INTRODUCTION

The purpose of this statistical analysis plan (SAP) is to provide a description of the statistical analyses performed for the Phase 2a protocol, ATI-502-AD-201, V1.0 (23Apr2018).

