### **4.3 Safety Analyses**

The comprehensive safety analysis is based on all subjects in the Safety population.

The following sections detail the summaries performed on the safety data. Additional data handling rules including those for imputation of partially missing dates will be provided in a separate SAP document pertaining to data handling and programming specifications.

The baseline scores for vital signs, laboratory assessments and ECGs will be the last non-missing value collected on or before the date of the first application of study medication. This baseline will also be used for calculating change from baseline.

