### **4.5 Changes in/ Clarifications to the Conduct of the Study or Planned Analysis**

In addition to the EASI-75 planned in the protocol, an EASI-50 has been added.

Sensitivity assessments of key efficacy analyses was included that was not specified in the protocol.

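### SAP 4.3.5 does not carry over the out-of-range laboratory counts that Protocol 14.1 plans for the primary safety outcome, and SAP 4.5 does not declare the departure

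*SAP*

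**What the plan says.** Protocol 6.1 makes safety and tolerability the primary outcome, and Protocol 14.1 treats safety parameters as the primary analysis variables. Section 14.1 then fixes the form of the laboratory summary: external laboratory data "will be summarized as binary outcomes based on the determination of values beyond applicable normal ranges", and in some cases by the clinical significance of the deviation. The synopsis says the same ("summarized as binary outcomes based on the determination of values beyond applicable normal ranges").

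SAP 4.3.5 reads: "Chemistry and Hematology parameters will be summarized using descriptive statistics for each visit". It continues: "Both actual values and changes from baseline will be summarized". It adds subject counts for two groups of criteria, hepatobiliary abnormality and potential renal impairment, and defines neither. It does not mention normal ranges, a laboratory shift table or clinical significance.

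SAP 4.3 introduces its subsections with "The following sections detail the summaries performed on the safety data". It also refers to a separate document, which it describes as covering data handling and programming specifications.

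SAP 4.5, the section for changes to the planned analysis, has two entries: "In addition to the EASI-75 planned in the protocol, an EASI-50 has been added", and the addition of efficacy sensitivity assessments.

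**The concern.** The protocol and the SAP describe different laboratory summaries for the primary outcome, and the section meant to record such differences does not record this one. A programmer following the SAP would not produce the counts that the protocol describes. A reader of the results would not be told that they had been planned.

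This is a single-arm study of 30 subjects with no inferential statistics, so subject counts are a large part of the safety evidence. Haematology is the most exposed area. The protocol sets hold and withdrawal limits on it, but SAP 4.3.5 plans no haematology count.

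**Working it through.** The plan gives no figure to reproduce, so the check is a comparison of texts followed by a count of what is affected.

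**1. Form of the laboratory summary**

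| Item | Protocol 14.1 and synopsis | SAP 4.3.5 |
|---|---|---|
| Main form | Binary, against normal range | Descriptive statistics of values and changes, by visit |
| Clinical significance | In some cases | Not mentioned |
| Subject counts | All external laboratory data | Hepatobiliary and renal criteria only |

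**2. Are the counts planned elsewhere in the SAP?** No other SAP section plans a normal-range count for laboratory data. SAP 4.3 says that its own subsections detail the safety summaries. The separate document is not available, and its stated scope is data handling and programming, so it cannot be assumed to hold these tables.

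**3. Does the protocol version explain it?** The SAP Introduction cites protocol V1.0, while the current protocol is V2.0. The V2.0 change table lists no change to Section 14, so the version difference does not account for the gap.

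**4. Is it a general preference for continuous summaries?** No. SAP 4.3.4 keeps a categorical shift from baseline to worst interpretation for the centrally processed ECGs. The gap is specific to laboratory data.

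**5. Parameters affected** (Protocol 13.1.6, each differential cell type counted once, red cell morphology left out as non-numeric)

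- Haematology: 5 counts or indices + 5 differential cell types = 10. None has a subject count in SAP 4.3.5.
- Chemistry: 21. If the undefined hepatobiliary and renal criteria use 4 to 6 of these (assumption), 21 − 6 = 15 to 21 − 4 = 17 have no count.
- Protocol Table 4: 7 hold criteria, of which 5 are haematological (white cells, neutrophils, lymphocytes, platelets, haemoglobin). The other 2 (AST or ALT, and creatinine) fall in the areas of the two planned counts.

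**6. What other tables recover**

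- *Adverse events.* Protocol 13.2.1.1 sends clinically significant findings before dosing to medical history and allows abnormal laboratory values to describe an AE. A clinically significant value after dosing should therefore reach the AE tables, though possibly under a diagnosis.
- *Disposition.* A value meeting a Protocol 9.3 limit leads to discontinuation, and SAP 4.1.2 tabulates reasons for discontinuation.
- *Exposure.* SAP 4.1.7 names no count of interruptions. A Table 4 hold that resolves, and is not reported as an AE, need not appear in any subject count.
- *Remainder.* Subjects with out-of-range values that are neither judged clinically significant nor at a 9.3 limit are not counted anywhere.

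**7. Can the descriptive rows give that number?** SAP 4.3.5 does not name its statistics. Suppose they include minimum and maximum, as in other SAP sections (assumption). A minimum below range shows that at least one subject was low at that visit, not how many were. Across visits, a low minimum at each of the 4 post-baseline visits fits one subject who is low four times (1/30 = 3.3%). It also fits four subjects who are low once each (4/30 = 13.3%), or more.

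**The case against.** The strongest reply is that little of consequence is lost. Clinically significant values should reach the AE tables, values at a 9.3 limit reach disposition, and the hepatobiliary and renal counts keep part of the binary approach for chemistry. The Table 4 and 9.3 limits act on individual results and do not depend on any table. No decision rule uses the missing counts, no collected data are lost, and Protocol 14.1 itself asks for clinical significance only in some cases. All of this stands, and it limits the severity. It does not answer the mismatch, because Protocol 14.1 bases the count on normal ranges and not on the investigator's judgement.

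A reader might infer three stronger things that the documents do not support.

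- *That the summary was deliberately removed.* SAP 4.3.5 is silent on it and Protocol 14.1 still stands. The evidence shows only that it was not carried over and not declared.
- *That a neutrophil or platelet value out of range after dosing must be treatment-emergent, because inclusion criterion 7 requires both to be normal.* Screening can precede dosing by up to 14 days, blood is drawn again at Visit 2, and the SAP baseline is the last value on or before the date of first application. A value could leave the range before treatment.
- *That the size of the hidden signal can be calculated.* The documents give no normal-range limits, so any constructed example depends on the limit chosen.

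**Conclusion.** The point holds as a contradiction between protocol and SAP on the primary outcome that SAP 4.5 does not declare. It should be fixed. Its size is the absence of a subject count in SAP 4.3.5 for all 10 numeric haematology parameters and, on the stated assumption about the undefined criteria, for 15 to 17 of the 21 chemistry parameters. The information lost is confined to out-of-range values that are not judged clinically significant and do not meet a 9.3 limit.

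The conclusion assumes that the separate programming document does not contain the counts, as its description suggests. It does not depend on which descriptive statistics are chosen.

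**What to change.** In SAP 4.3.5, add for each chemistry and numeric haematology parameter the number and percentage of Safety Population subjects below and above the laboratory's normal range. Show this at baseline, at each post-baseline visit and at any post-baseline visit. Give clinical significance where it is assessed, and say for which parameters that is. Keep the descriptive statistics and name them. List any remaining departure from Protocol 14.1 in SAP 4.5, with the reason.

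The cost is SAP wording and programming on central laboratory data already collected, with no new visits, samples or subjects. The tables become longer: 31 parameters × 2 directions × 6 columns (baseline, 4 post-baseline visits, any) = 372 cells, of which 10 × 2 × 6 = 120 are haematology. Some values will be out of range by chance, so the counts should be read beside the baseline column and the AE tables.

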### **4.4 Sample Size**

Sample size for this study was not based upon formal statistical criteria. A total of 30 subjects is planned.

### **4.5 Changes in/ Clarifications to the Conduct of the Study or Planned Analysis**

In addition to the EASI-75 planned in the protocol, an EASI-50 has been added.

Sensitivity assessments of key efficacy analyses was included that was not specified in the protocol.

## **5. STATISTICAL SOFTWARE**

All data summaries and listings will be performed using SAS® Version 9.2 or higher, under Windows operating system.
